The NOAEL reported in the 28-day repeat dose toxicology studies in rat and dog (Beagle) was 50 mg/kg/day in rat and 15 mg/kg/day in dog which is equivalent to a human equivalent dose (HED) of the free base equivalent of 8.1 mg/kg/day and 8.3 mg/kg/day, respectively. Based on a maximum recommended starting dose (MRSD) of 1/10th of the NOAEL and using the most conservative approach, an MRSD of 0.81 mg/kg of free base which is equivalent to 1.2 mg KNX100 phosphate per kg per day. Assuming an average human weight of 60 kg, this would equate to a clinical starting dose of ~72 mg/day.

However, the severity, reversibility, and monitorable nature of the toxicity defining the NOAEL impacts how it influences the selection of the safe starting dose. Respiratory effects (decreased tidal and minute volume premonitory to decreased respiration rate in the rat) and central nervous system (CNS) effects (decreased body temperature and hypoactivity premonitory to convulsions in the rat; tremor, ataxia and hypoactivity premonitory to convulsions in the dog) both inform the selection of the safe starting dose. The severity of the CNS effects and trend towards greater-than-dose-proportional KNX100 exposure suggest a minimum of a 10-fold dose margin relative to the CNS effect threshold is appropriate to be protective of patient health. CNS effects, therefore, serve as the primary basis for selection of the starting and escalating clinical dose regimens.

The selection of the starting dose for human studies was based on the CNS NOEL determined in the 28-day dog toxicology study. In the dog, the CNS NOEL dose (7.5 mg free base/kg) corresponded to a HED of 6 mg KNX100 phosphate/kg. Therefore, 1/10th of this value is equivalent to 0.6 mg KNX100 phosphate/kg, or 36 mg KNX100 phosphate in a 60 kg subject which would be the maximum recommended starting dose.

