6.21. Removal of Subjects from the Study or Study Drug

6.21.1. Criteria for Discontinuation or Withdrawal of a Subject

The primary reason for discontinuation or withdrawal of the subject from the study should be recorded in the eCRF, using the following categories:

- Voluntary withdrawal by subject decision
 - The subject is at any time free to withdraw his or her participation in the study, without prejudice and independent of any decision concerning participation in other aspects of this study.
- AE
 - The subject has experienced an AE that requires early termination because continued participation imposes an unacceptable risk to the subject's health, or the subject is unwilling to continue because of the AE.
- Vital signs
 - Measurement of abnormal and out of range parameters on repeat analysis as required (postdose):
 - O₂ saturation of <90% for 60 seconds or longer
 - Respiratory rate of <8 breaths/minute for 2 or more minutes
 - Heart rate of <50 bpm
 - Systolic blood pressure of ≤80 mmHg
 - Temperature of ≤32°C
- EEG
 - Evidence of the emergence of epileptiform discharges as evaluated by an epileptologist or a Level 3 ANZAN certified neurologist.
- ECG
 - QTcF duration >475 ms and increase exceeding 40 ms in males
 - QTcF duration >475 ms and increase exceeding 60 ms in females
- Thyroid function tests outside the normal reference ranges (and upon repeat) and CTCAE Grade 2 or above. That is, symptomatic and requiring treatment.
- Laboratory Parameters
 - Safety laboratory tests that are outside the normal reference ranges (and upon repeat) and deemed clinically significant by the study PI.

- Pretreatment event
 - The subject has a pretreatment event that requires early termination because continued participation imposes an unacceptable risk, or the subject is unwilling to continue due to the pretreatment event.
- Pregnancy
 - If the subject is found to be pregnant, the subject must be withdrawn immediately.
- Major protocol deviation as judged by the investigator and/or Kinosis.
 - The discovery post-randomization that the subject was incorrectly initiated on investigational drug, failed to meet protocol entry criteria, or did not adhere to protocol requirements **and** continued participation poses an unacceptable risk to the subject's health.
- Compliance
 - The subject has poor compliance with study drug or study procedures.
- Additional treatment

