8.5. Study Endpoints

8.5.1. Primary Safety Endpoints

The primary safety endpoints include:

- Incidence of TEAEs and TESAEs, related AEs, AEs leading to discontinuation, and AEs by severity.
- Clinical laboratory testing from protocol-specified standard urine and blood tests, including liver function tests (LFTs) and thyroid function tests (TFTs: triiodothyronine [T3], thyroxine [T4], thyroid stimulating hormone [TSH]).
- Change in clinical observations from baseline, including body temperatures, vital signs, ECGs, EEGs.

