⁶ Vital signs collection includes systolic and diastolic blood pressures, pulse rate and body temperature which will be measured with the subject to be seated or semi-supine after resting for at least 3 minutes. Vital signs also include respiratory rate, continuous pulse oximetry and saturated oxygen, which will be undertaken via telemetry within 2 hours predose and at 30 hours (\pm 30 minutes) after dosing. Measurements of all vital signs will be recorded within 1 hour predose, and at 30 minutes, 1-, 1.5-, 2-, 4-, 6-, 8-, 12-, 24- and 30-hours postdose (\pm 15 minutes). Peak flow measurement will also be undertaken within 1 hour predose as well as at 1-, 2-, and 4-hours (\pm 15 minutes) postdose. The highest of 3 peak flow measurements, at each timepoint, shall be recorded.

⁷ Subjects should fast overnight prior to collection of laboratory tests at Screening. The Day 1 laboratory tests will be undertaken at 1 hour postdose (\pm 15 minutes) and at 24 hours (\pm 15 minutes) postdose (Day 2).

⁸ The Day 1 urinalysis tests will be undertaken at 1-hour postdose (\pm 60 minutes) and at 24 hours (Day 2) (\pm 60 minutes) postdose.

⁹ Serum pregnancy test at Screening and End of study visit. A urine pregnancy test will be conducted in women of child-bearing potential on admission to unit on Day -3.

¹⁰ Test may be repeated if required.

¹¹ Each subject will receive study drug based on randomization (placebo or KNX100), after a 10 hour fast.

¹² Please refer to [Appendix 3](#) for information related to PK assessments and sampling times.

¹³ Plasma samples for biomarker analyses will be collected predose (Day -1), on Day 1 at 1-hour postdose (\pm 15 minutes), and at EOS/EOT.

¹⁴ EEG: Please refer to [Appendix 3](#) for information related to EEG assessments.

¹⁵ Please refer to [Appendix 3](#) for information related to ECG assessments which will be performed in triplicate. The timing and number of ECGs may be altered, depending on the emerging PK and safety profile. Additional ECGs should also be collected if a subject experiences a cardiac adverse event.

¹⁶ Participants will be admitted to the Phase 1 unit on Day -3 so they can sleep for 4 hours prior to undertaking their sleep deprived EEG on Day -2, through to 30 hour testing on Day 2.

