5.4 Visit Windows

Data will be summarized using the recorded nominal visit values in the CRF; no visit date windowing will be conducted. Unscheduled visit data may be included in summaries of baseline, minimum/maximum post-baseline, and incidence of subjects with potentially clinically significant post-baseline results. Unscheduled visits will also be presented in applicable data listings.

In general, if multiple non-missing values are available at the same visit/timepoint then the later value will be used in the analysis. In cases where multiple non-missing values are on the same date and time, the value with the larger Study Data Tabulation Model (SDTM) record sequence number will be used in the analysis.

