6.4.3 Vital Signs

Vital signs and body measurements include: height (cm); weight (kg); BMI (kg/m²); systolic and diastolic blood pressure (mmHg); heart rate (beats/min); respiratory rate (breaths/min); oxygen saturation (%); temperature (°C); and the highest of 3 peak flow measurements (L/min) taken on Day 1 will be recorded on the CRF. Observed values and changes from baseline for vital signs will be summarized by study part and cohort at each visit and time point.

Potentially clinically significant post-baseline results will be summarized by study part and cohort at each visit and timepoint.

Vital Sign	Criteria
Systolic BP	> 150 mmHg > 200 mmHg ≤ 80 mmHg
Diastolic BP	> 100 mmHg > 110 mmHg
Heart Rate	< 50 bpm > 120 bpm ≥ 30 bpm increase from baseline ≥ 30 bpm decrease from baseline
Respiratory Rate	< 8 breaths/min > 24 breaths/min
Oxygen Saturation	< 95%
Temperature	> 38.3°C increase of ≥ 1.1°C from baseline

All vital signs results will be provided in by-subject data listings.

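### The vital-sign flag table in SAP 6.4.3 counts temperature rises only, so a fall, which is the nonclinical signal and a protocol withdrawal limit, cannot be counted there

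*SAP*

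**What the plan says.** SAP 6.4.3 plans two kinds of vital-sign summary. The first gives observed values and changes from baseline at each visit and timepoint. The second counts results that meet listed criteria for potential clinical significance. For temperature those criteria are "> 38.3°C increase of ≥ 1.1°C from baseline". Systolic pressure, heart rate, respiratory rate and oxygen saturation each have a low-side criterion, and heart rate also has a decrease-from-baseline criterion. Respiratory rate, for example, is flagged in both directions: "< 8 breaths/min > 24 breaths/min".

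Three protocol sections bear on the direction of interest for temperature:

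- Section 3.2.1 lists, among the findings that inform the safe starting dose, "decreased body temperature and hypoactivity premonitory to convulsions in the rat" and "decreased tidal and minute volume premonitory to decreased respiration rate in the rat".
- Section 6.21.1 includes "Temperature of ≤32°C" among the postdose vital-sign limits for withdrawal. It gives no high-temperature limit.
- Section 8.5.1 has as a primary safety endpoint: "Change in clinical observations from baseline, including body temperatures, vital signs, ECGs, EEGs".

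**The concern.** A table of notable values should be able to show the effect that the trial has reason to look for. Section 3.2.1 names a decrease in two vital signs measured in this study, respiratory rate and body temperature. The SAP gives the first a low-side row and the second none.

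The table was not built for high values only, since four of its six parameters have a low-side row. Diastolic pressure also lacks one, but it has no withdrawal limit in section 6.21.1 and is not named in section 3.2.1. The SAP gives no reason for treating temperature differently.

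What is at stake is how a zero is read. The clinical study report will contain a table that singles out individual values for a primary safety endpoint. For falls in temperature, that table will show zero whatever happens, and a reader could take the zero as reassurance.

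**Working it through.** The plan states no figure to reproduce. The check is one of coverage.

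**Inputs.** Temperature criteria >38.3°C and rise ≥1.1°C (SAP 6.4.3); normal oral temperature 35.5-37.5°C (protocol Appendix 4); withdrawal limits (protocol 6.21.1); timed vital signs in Part A "at 30 minutes, 1-, 1.5-, 2-, 4-, 6-, 8-, 12-, 24- and 30-hours postdose" (protocol Appendix 1); 6 active subjects per cohort and 4 planned Part A cohorts (protocol 3.1).

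**Step 1: can a fall be flagged?** Let B be a baseline between 35.5 and 37.5°C, and T a later reading below B.

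- T < B ≤ 37.5 < 38.3, so the absolute criterion fails.
- T − B < 0 < 1.1, so the change criterion fails.

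The two criteria are printed together without an *and* or an *or*, but the result is the same under either reading. A grid in 0.1°C steps agrees. Taking 21 baselines from 35.5 to 37.5°C and every lower value down to 30.0°C gives 55 + 56 + … + 75 = 21 × 65 = 1,365 falls, of which 0 are flagged. A fall to 32.0°C from 35.5, 36.5 or 37.5°C is a change of −3.5, −4.5 or −5.5°C, and none of these is flagged. The qualifier about a normal baseline matters, because a febrile baseline could fall and still exceed 38.3°C.

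**Step 2: withdrawal limits against SAP rows, timed readings only.**

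| Vital sign | Protocol 6.21.1 | SAP 6.4.3 low-side row |
|---|---|---|
| Oxygen saturation | <90% for ≥60 s | <95% |
| Respiratory rate | <8/min for ≥2 min | <8/min |
| Heart rate | <50 bpm | <50 bpm |
| Systolic pressure | ≤80 mmHg | ≤80 mmHg |
| Temperature | ≤32°C | none |

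A reading at the limit would be counted for 4 of the 5 signs; temperature is the exception. The comparison does not cover the duration conditions or continuous monitoring, because SAP 6.4.4 sends telemetry to listings only.

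**Step 3: how many readings are affected?** Part A has 10 timed postdose readings, so 10 × 6 × 4 = 240 planned active-arm readings, none of which can be counted as a fall. This leaves out the follow-up visit and all of Part B. It measures coverage, not events. The documents give no rate of temperature falls, and none is assumed.

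**Step 4: do the by-timepoint summaries replace the count?** Suppose one of six active subjects falls by 3.0°C at a timepoint and the other five do not change. The mean change is −3.0/6 = −0.5°C, the median is 0.0 and the minimum is −3.0. The fall is visible as a minimum, but subjects with a fall are not counted, and falls in different subjects at different timepoints are not added up.

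**Step 5: what would a mirrored row catch?** A decrease of ≥1.1°C flags readings at or below 34.4, 35.4 and 36.4°C for baselines of 35.5, 36.5 and 37.5°C. It also flags any reading of 32.0°C or lower from an Appendix 4 baseline, since the smallest such drop is 35.5 − 32.0 = 3.5°C.

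**The case against.** The strongest reply is that the analysis the protocol asks for is already planned. Protocol 8.6 requires results and changes from baseline to be tabulated and listed, and it asks for no vital-sign threshold table. SAP 6.4.3 provides the changes, and SAP 5.1 includes the minimum and quartiles. With six active subjects per cohort, a large fall stands out as the minimum at its timepoint. A fall judged clinically significant becomes an adverse event (protocol 6.17) and is counted by subject, and one that leads to withdrawal is counted under SAP 6.1.1. This stands, and it limits the point to the counts in one table.

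Second, nothing obliges the SAP table to mirror section 6.21.1. Only heart rate and systolic pressure match it exactly, and the table is selective elsewhere, with no low diastolic row and no peak-flow row. This is also true, but those gaps do not coincide with a named nonclinical decrease and a withdrawal limit. Temperature does.

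Third, the temperature fall is a rat finding. For the dog, section 3.2.1 lists tremor, ataxia and hypoactivity, and dog data set the starting dose and the exposure cap. Seizure and interictal activity on EEG are counted under SAP 6.4.6. This lowers the weight of the signal but does not remove it, since section 3.2.1 says that CNS effects in both species inform the starting dose.

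Fourth, no document supports 1.1°C as a meaningful fall. A mirrored row would flag 36.6 to 35.5°C, which ends inside the Appendix 4 range, and would miss 36.0 to 35.0°C, which ends below it. That is fair. The 1.1°C is the SAP's own increment for a rise, applied in the other direction, and a rise from 36.4 to 37.5°C is already flagged while ending inside the range.

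**Conclusion.** The point holds. For any baseline in the Appendix 4 range, the SAP 6.4.3 flag table can return only zero for falls in temperature, including a fall to the protocol's own withdrawal limit. The conclusion rests on the printed criteria and the normal range alone, and needs no assumption about event rates.

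Its consequence is modest. It does not leave subjects unprotected: the Cohort Review Committee reviews vital signs directly (protocol 5.3.4) and does not depend on this table. Nor are data lost. What is missing is a subject count, in the table meant for notable values, for the direction of change named in the protocol. Because the correction is so cheap, it should be made.

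**What to change.** In SAP 6.4.3, add one temperature row: a decrease of ≥1.1°C from baseline, mirroring the existing increase criterion. This is an analysis flag and sets no clinical rule. If an absolute low-temperature row is also wanted, the sponsor should choose it and reconcile it with the lower end of the Appendix 4 range (35.5°C) and the limit in protocol 6.21.1 (≤32°C).

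A minor companion change is to add a count of subjects who meet each criterion at any post-baseline time, including repeat and unscheduled readings. Protocol 6.5 has out-of-range vital signs repeated, and SAP 5.4 keeps the later of several values at a timepoint, so a qualifying first reading could otherwise drop out. SAP 5.4 already permits the wider data: "Unscheduled visit data may be included in summaries of baseline, minimum/maximum post-baseline, and incidence of subjects with potentially clinically significant post-baseline results". The by-timepoint summaries can stay as they are.

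The cost is one criterion row, one subject-count row and minor programming, with no new data. Some transient readings will be flagged, and a 1.1°C fall from a baseline of 36.6°C or higher (35.5 + 1.1) ends at or above the lower Appendix 4 limit. The existing rise criterion has the same property from 36.4°C or lower (37.5 − 1.1).

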6.4.4 Telemetry

Telemetry results will be presented in by-subject data listings.

6.4.5 Electrocardiogram (ECG)

Electrocardiogram (ECG) parameters include: HR (beats/min), PR interval (msec), RR interval (msec), QRS duration (msec), QT interval (msec), QTcB interval (msec), QTcF interval (msec), P wave (msec), and T wave (msec). Observed values and changes from baseline for ECG parameters

will be summarized by study part and cohort at each visit and time point. If triplicate reads are taken, the mean of the reads will serve as the observed value at the specific visit and timepoint.

Investigator-reported ECG findings shifts from baseline to each post-baseline visit/timepoint and maximum post-baseline will be summarized by study part and cohort. Categories of Normal, Abnormal – Not Clinically Significant, and Abnormal – Clinically Significant will be included.

Subjects meeting the following potentially clinically significant criteria post-baseline will also be presented:

- 450 msec < QTcF / QTcB ≤ 480 msec
- 480 msec < QTcF / QTcB ≤ 500 msec
- 500 msec < QTcF / QTcB
- 30 msec < QTcF / QTcB change from baseline ≤ 60 msec
- 60 msec < QTcF / QTcB change from baseline

All ECG parameter results will be provided in by-subject data listings.

6.4.6 Electroencephalogram (EEG)

Frequency and percentage of subjects showing any seizure activity and any interictal epileptiform activity in EEG results will be summarized by study part and cohort at each visit and timepoint. All EEG results recorded on the CRF will be presented in by-subject data listings.

6.4.7 Gastrointestinal Symptoms

Frequency and percentage of subjects in Part B (MAD) cohorts experiencing any gastrointestinal symptoms will be summarized by study part and cohort at each visit and any post-baseline. All gastrointestinal symptom assessment results recorded on the CRF will be presented in by-subject data listings.

Gastrointestinal symptom assessments will not be performed for Part A (SAD) subjects.

6.4.8 Columbia Suicide Severity Rating Scale (C-SSRS)

At the Screening Visit, the Baseline/Screening Version of the C-SSRS will be administered to Part B (MAD) subjects to assess lifetime and recent history. The Since Last Visit Version of the C-SSRS will be administered to subjects at each subsequent visit (Day 4 and Day7).

Data from the Baseline/Screening Version and from the Since Last Visit Version of the C-SSRS will be summarized by cohort. The number of subjects with any post-baseline occurrence of suicidal ideation (C-SSRS items 1-5), suicidal behavior (C-SSRS items 6-11), as well as occurrence of individual items at each visit will be summarized by study part and cohort.

C-SSRS results will be presented in by-subject data listings.

C-SSRS assessments will not be collected for Part A (SAD) subjects.

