6.7. Columbia Suicide Severity Rating Scale (C-SSRS)

The C-SSRS is a questionnaire used for suicidality assessment developed by multiple institutions, including Columbia University. The scale is evidence-supported and is part of a US national and international public health initiative involving the assessment of suicidality. The scale has been successfully implemented across many settings, including schools, college campuses, military, fire departments, the justice system, primary care and for scientific research. The C-SSRS Risk Assessment version is intended to help establish a person's immediate risk of suicide and is used in acute care settings.

The C-SSRS will be administered at screening and again at Day 4 and Day 7 postdose during the MAD part of the study. Please refer to the SOA in [Appendix 2](#) for details regarding timing for assessments.

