¹⁴ Please refer to [Appendix 3](#) for information related to ECG assessments. ECGs will be undertaken in triplicate. The timing and number of ECGs may be altered, depending on the emerging PK and safety profile. ECGs should also be collected if a subject experiences a cardiac adverse event.

¹⁵ EEG: Please refer to [Appendix 3](#) for information related to EEG assessments.

¹⁶ C-SSRS: will be administered predose at screening and then within 4 hours post the morning dose on Days 4 and 7.

¹⁷ Subjects will be admitted to the unit on Day -3 to undertake their sleep deprived EEG. Subjects will remain in the unit during the entire dosing phase and be discharged after collection of Day 8 assessments.

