5.2 General Definitions

Variable	Definition
Study Day	
 • Study Day = date of interest – treatment start date + 1, when the date of interest \geq treatment start date; • otherwise, Study Day = date of interest – treatment start date. 
Note: if either date is missing, Study Day calculations will not be performed. Should imputation be performed, then Study Day may be computed, where appropriate.

Baseline	
For ECG data, baseline is defined as the average of up to three measurements taken at the pre-dose timepoint on the Day 1 Visit if available; otherwise, baseline is defined as the last single tracing measurement taken prior to the first dose of study treatment.
 
For EEG data, baseline is defined as the assessment collected at the Screening Visit (Day -2) in which the patient was in a sleep deprived state.
 
For all other endpoints, baseline is defined as the last non-missing value collected prior to receiving the first dose of study treatment (based on date and time of administration as applicable). For endpoints with both planned pre-dose and post-dose timepoint assessments on Day 1, only pre-dose assessments will be considered as a candidate for baseline. For MAD Cohort 3, vital signs

	assessments on Day 1 associated with the second dose (i.e., evening) will not be considered as a candidate for baseline.
Post-baseline	Defined as values collected after receipt of the first dose of study treatment (based on date and time of administration as applicable)
Change from Baseline	Defined as: Post-baseline value – Baseline value
Duration on Study (in days)	End of study date – randomization date + 1
BMI (kg/m ²)	BMI is collected in the clinical database
Age (yr)	Age is collected in the clinical database
Study Completion	Defined as attendance at the End of Study (EOS) Visit.

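### In Part B, 39% to 90% of the Day 4 C-SSRS recall period can precede the first dose, yet the form counts as post-baseline; no form comes later than 4 hours after the Day 7 morning dose.

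*SAP*

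**What the plan says.** The protocol (6.7) sets the schedule: "The C-SSRS will be administered at screening and again at Day 4 and Day 7 postdose during the MAD part of the study". Footnote 16 of Appendix 2 adds the clock time: "C-SSRS: will be administered predose at screening and then within 4 hours post the morning dose on Days 4 and 7". In the Appendix 2 grid the Screening column runs from Day -28 to Day -2. The C-SSRS row has no mark at Day -1, Day 1, Day 8 or Day 14.

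SAP 6.4.8 gives Part B subjects the Baseline/Screening version at Screening, and then: "The Since Last Visit Version of the C-SSRS will be administered to subjects at each subsequent visit (Day 4 and Day7". The planned table is: "The number of subjects with any post-baseline occurrence of suicidal ideation (C-SSRS items 1-5), suicidal behavior (C-SSRS items 6-11"), plus individual items at each visit.

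SAP 5.2 defines post-baseline as: "Defined as values collected after receipt of the first dose of study treatment (based on date and time of administration as applicable"). The test is the moment of collection. Neither document says how to treat a form whose recall period starts before the first dose, and neither defines the last visit for this scale.

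**The concern.** A Since Last Visit questionnaire reports on an interval, whereas the SAP classifies it by the date on which it is completed. For most endpoints that distinction does not matter, because a blood pressure taken on Day 4 describes Day 4. Here the Day 4 form can describe up to four weeks before dosing together with three days on treatment, and the table puts the whole interval in the post-baseline column.

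At stake is how one or two events are read. Part B plans 24 subjects, 18 on active drug and 6 on placebo, with 6 active subjects per cohort. Events on this scale should be few in healthy volunteers screened for psychiatric illness, so a single wrongly classified subject could be the entire signal in a cohort. The error can run in either arm.

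The end of the schedule has a separate, smaller gap. Subjects are seen on Day 8 and again on Day 14, but the scale is given at neither visit.

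**Working it through.** The documents give no figure for this point, so there is none to reproduce. The check is a count of days.

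**Inputs**
- Screening C-SSRS on Day -k, with k from 2 to 28 (Protocol Appendix 2).
- There is no Day 0. For dates before treatment start, SAP 5.2 has: "otherwise, Study Day = date of interest – treatment start date". Day -k is therefore k days before the first dose, and Day 4 is 3 days after it.
- The Day 4 form is completed h hours after the morning dose, with h from 0 to 4 (Appendix 2, footnote 16).
- Assumptions: the last visit is the last C-SSRS administration, and the Screening form is completed at about the same clock time as the morning dose.

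**Pre-dose share of the Day 4 recall** = k / (k + 3 + h/24)

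| Screening form | h = 0 | h = 4 |
|---|---|---|
| Day -28 | 28/31.00 = 90.3% | 28/31.17 = 89.8% |
| Day -14 | 14/17.00 = 82.4% | 14/17.17 = 81.6% |
| Day -7 | 7/10.00 = 70.0% | 7/10.17 = 68.9% |
| Day -3 | 3/6.00 = 50.0% | 3/6.17 = 48.6% |
| Day -2 | 2/5.00 = 40.0% | 2/5.17 = 38.7% |

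The range is about 39% to 90%, depending on when within the window the subject was screened. The Day 7 form is not affected: its recall runs from Day 4 to Day 7, all after the first dose.

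**Alternative anchors for the Day 4 recall**
- Form on Day -1: 1/4.00 = 25.0% to 1/4.17 = 24.0% pre-dose.
- Form at Day 1 predose: about 0%.

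**Weight of one subject**: 1/6 = 16.7% of a cohort's active arm.

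**Time after the last form** (0 to 4 h after the Day 7 morning dose)
- To the 24-hour assessments on Day 8: 24 - 0 = 24 h down to 24 - 4 = 20 h.
- To Day 14: 7 - 4/24 = 6.8 to 7 days. With the ±2-day window: 5 - 4/24 = 4.8 to 9 days.
- Cohort 3: the second dose is 8 h (±30 min) after the first (Protocol 5.3.3). The last form therefore precedes the last dose by at least 7.5 - 4 = 3.5 h.

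**If the last visit meant the previous inpatient day**, the Day 4 form would reach back only to Day 3 and the Day 7 form only to Day 6. The pre-dose share would vanish, but Days 1, 2 and 5 would be covered by no form. The two defects are alternatives; they do not add up. The wording of SAP 6.4.8, which lists Day 4 and Day 7 as the subsequent visits, favors the first reading.

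**The case against.** The best case for the plan is that timing information exists elsewhere. Part B subjects are inpatients from Day -3, and Appendix 2 states: "Subjects will remain in the unit during the entire dosing phase and be discharged after collection of Day 8 assessments". Adverse events are collected at Screening, on Day -1, on every dosing day, on Day 8 and on Day 14. Protocol 6.17 extends adverse event recording to findings from any safety-relevant assessment. SAP 6.4.1 and Appendix 1 decide treatment emergence by event start date, and C-SSRS results are also listed by subject. So a reader might infer that a positive Day 4 form could never be dated, or that the follow-up week has no safety assessment. Neither follows. What stands is narrower: adverse event dating does not feed the C-SSRS table, and nothing requires onset relative to the first dose to be recorded for this scale.

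The scale is also not a listed primary endpoint and is not named among the CRC escalation criteria. The analysis is descriptive, and Protocol 4.3 excludes significant psychiatric disorder. That limits the importance of the point but does not make the label correct.

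Two further readings should be set aside. One is that no form is given after the Day 7 morning dose. Protocol 6.7 and footnote 16 place the Day 7 form after that dose, and in Cohorts 1 and 2 (16 of 24 subjects) it is the last dose. The other is that 90% is the typical share, or the chance of misclassification. It is the maximum share of days; the documents give no event rate and no distribution of screening dates.

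**Conclusion.** The point holds as a classification fault in one safety table, together with a smaller gap at the end of the schedule. Followed as written, the plan counts ideation or behavior that occurred between Screening and the first dose as a post-baseline occurrence if it is first reported on Day 4. The part of the Day 4 recall exposed to this is about 39% to 90% of its length, on the assumption that the last visit is the last C-SSRS. How many subjects would be affected cannot be estimated from the documents; one would be 16.7% of a cohort's active arm.

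The scale is not given later than 4 hours after the Day 7 morning dose. That leaves Cohort 3's final dose and the following 5 to 9 days or so to general adverse event collection alone.

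This is a worthwhile, inexpensive correction. It does not threaten the primary safety conclusions.

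**What to change.** 1. In Protocol 6.7, Protocol Appendix 2 and SAP 6.4.8, add a Since Last Visit C-SSRS at Day 1 predose and name it as the baseline reference. SAP 5.2 already takes the last value before the first dose as baseline, so the general definition need not change. Day -1 is not an adequate substitute, since about a quarter of the Day 4 recall would remain pre-dose.
2. In SAP 6.4.8, define the last visit as the last C-SSRS administration, and count as post-baseline only forms whose recall starts at the Day 1 predose form or later.
3. If Part B data are already collected, count an occurrence as post-baseline only when its onset is on or after the first dose, and footnote the Day 4 recall period in the table. State a rule for unknown onset; for adverse events, SAP Appendix 1 sets a wholly missing start date to the first dose date, and the same convention could be used.
4. Optionally, add the same form at the existing Day 14/ET visit. This would also cover the time after Cohort 3's last dose.
5. Reconcile the version of the instrument. Protocol 6.7 describes the Risk Assessment version, while SAP 6.4.8 names the Baseline/Screening and Since Last Visit versions. The recall argument rests on the SAP's choice.

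The cost is one short questionnaire per Part B subject, or two with the Day 14/ET form, at contacts that already exist, plus wording changes in both documents. Item 3 needs no new visits, only a check of source records for any positive Day 4 form.
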